6.1.9. Data Adjustments/Handling/Conventions

All collected data will be presented in listings. Data not subject to analysis according to this plan will not appear in any tables or graphs but will be included only in the data listings.

All P values will be displayed in four decimals and rounded using standard scientific notation (e.g., 0.XXXX). If a P value less than 0.0001 occurs it will be shown in tables as <0.0001.

AEs and medical histories will be coded using the latest version of the Medical Dictionary for Regulatory Activities (MedDRA) thesaurus available at time of programming.

[figure not shown]
If partial dates of AEs occur, the convention for replacing missing dates for the purpose of TEAE is as follows: if just day is missing then the day assigned is the first day of the month or the date of first dose (if in the same month), whichever is later; if just month is missing then the month assigned is the month of the first dose, unless that results in a date prior to the first dose in which case the month after the first dose is used; and if both month and day are missing then the month assigned is the month of the first dose and the day assigned is either the first day of the month or the first dose date, whichever is later.

If partial times occur, the convention is as follows: if the missing time occurs on the day of the first dose and both the hour and minute are missing then the time assigned is the time of the first dose, otherwise if both the hour and minute are missing and the date is not the date of first dose the time assigned is 12:00; if the date is the same as the date of the first dose and only hour is missing the hour assigned is 12 or the hour of first dose, whichever is later, and if the date is the same as the date of first dose and only the minute is missing the minute assigned is 30 or the minute of first dose, whichever is later. Otherwise the hour assigned is 12 if the hour is missing and the date is not the same as the date of first dose and the minute assigned is 30 is the the date is not the same as the date of first dose.

These conventions will be applied only to AE onset dates and times with the following precaution: if the missing date and time reflect the date and time of onset of an AE, the modified date and time will be constructed to match the first documented date/time post drug administration while preserving the order in which the AE was reported in the eCRF.

In general, for quantitative laboratory values reported as ' \leq X' or ' \leq X', the LLOQ will be used

AD-ST-33.06 Effective date: 12-Nov-2020

for analysis (i.e., the value of X will be used in the analysis for lab values reported as '<X' or ' \le X'). Similarly, for quantitative laboratory values reported as '>X' or ' \ge X', the upper limit of quantification (ULOQ) will be used for analysis (i.e., the value of X will be used in the analysis for lab values reported as '>X' or ' \ge X').

For analysis purposes, repeat laboratory test results will not be used unless the original laboratory value is missing or indicated as invalid, in which case the first non-missing repeated laboratory value will be used for data analysis.

ADA titre reported as <30 (below the minimum required dilution) is a negative result for the presence of ADA.

For descriptive statistics of serum concentration summaries:

- At a time-point where less than or equal to 50% of the values are not quantifiable (NQ, below LLOQ), all NQ values will be set to the LLOQ, and all descriptive statistics will be calculated accordingly.
- If more than 50%, but not all, of the concentrations are NQ, the geometric mean, geometric mean ± geometric SD and gCV% will be reported as not calculable (NC). The maximum value is reported from the individual data, and the minimum and median are set as NO.
- If all concentrations are NQ at a time-point, the geometric mean, minimum, median and maximum are reported as NQ and the gCV% and geometric mean ± geometric SD as NC.

7. Study Patients/Subjects and Demographics

7.1. Disposition of Patients/Subjects and Withdrawals

The total number of subjects for each of the following analysis populations will be presented for the Screening Population by randomized treatment group and overall:

[figure not shown]
- Screening Population
- Safety Population
- mITT Population
- Included in the mITT population
 - Evaluable Week 12 efficacy
 - Evaluable LOCF efficacy
- Not efficacy evaluable
- PK Population

For the Screening Population, disposition will include tabulation of:

- the number of screened subjects
- the number of re-screened subjects
- the number of enrolled subjects

The output will be further presented by treatment group and overall summarising:

AD-ST-33.06 Effective date: 12-Nov-2020

- the number of randomized subjects
- the number of subjects who completed study treatment
- the number of completed subjects
- the number of subjects withdrawing (discontinued)
- the reasons for discontinuation from study treatment and withdrawal from the study.

For all categories of subjects by treatment group, percentages will be calculated using the number of subjects randomized as the denominator.

7.2. Protocol Deviations

Major protocol deviations, as determined by a Sponsor blinded review of the data prior to database lock and unblinding of the study will be reported in listings.

The Sponsor or designee will be responsible for producing the final deviation file. This file will be finalized prior to database lock, and all information will be included in the SDTM.DV domain (deviations domain).

All protocol deviations will be presented in a data listing, with a flag to indicate if a deviation was considered major.

A summary table by treatment group and overall will be generated based on protocol deviation severity (minor/major) and the classification of protocol using the following categories:

[figure not shown]
- Inclusion
- o Exclusion
- Study drug
- Assessment safety
- Assessment– efficacy
- Lab/endpoint data
- Visit window
- Informed consent
- o Prohibited co-medication
- o Overdose/misuse
- o Other

7.3. Demographics and Other Baseline Characteristics

Descriptive summaries of the demographic and other baseline characteristics will be presented for all analysis populations. All demographic and baseline characteristics will be presented both overall and by treatment group.

The following demographic and baseline data will be presented in tables:

AD-ST-33.06 Effective date: 12-Nov-2020

- Demographics: age, gender, ethnicity, race, height, weight, and body mass index (BMI)
- For female the number and percentage of women surgically sterile and postmenopausal will be described.
- Diagnosis of osteoarthritis: number of subjects with osteoarthritis diagnosis and area affected, clinical significance, radiological investigations, radiological significance, Kellgren-Lawrence score.

The number and percent of subjects reporting various medical histories, grouped by MedDRA system organ class (SOC) and preferred term (PT), will be tabulated by treatment group.

This analysis will be conducted for the Safety Population.

7.4. Exposure

The following parameters of study drug exposure and compliance will be summarized by treatment group for the Safety Population:

- Maximum number of doses administered
- Total duration of exposure
- Total (cumulative) dose infused

In addition, any incomplete infusions will be listed.

8. Efficacy Analysis

All efficacy variables will be summarized descriptively including number of observations, number of missing values, mean, SD, minimum, median, and maximum for continuous variables, and frequency of observations in each category and percentage for categorical variables.

Primary and secondary endpoint efficacy data will be tabulated according to the observed cases, LOCF, and BOCF approaches.

[figure not shown]
8.1. Primary Efficacy Analysis

The primary efficacy endpoint of this study is the change in the weekly average of the average daily pain scores from the baseline week to Week 12 measured on an 11-point (0-10) NRS.

MCP-Mod approach. The main statistical analysis of the primary efficacy endpoint will use the MCP-Mod approach on LOCF data, which is a well-established statistical methodology for establishing both the existence of a dose response and modelling the underlying dose-response relationship. The modelling step ('MOD' step) from the MCP-MOD approach will only be conducted if stage 4 is initiated, otherwise there would be insufficient dosing data to fit the non-linear models.

There are two steps to MCP-Mod:

AD-ST-33.06 Effective date: 12-Nov-2020

- 1. The 'MCP' step is a rigorous method to establish presence of a dose response while protecting the type I error and, if the dose-response relationship is statistically significant, then
- 2. The 'MOD' step estimates the dose response function and associated model parameters.

The MCP test will use linear contrasts corresponding to the five candidate models described in Section 3.2. The test will use pre-specified model parameters and optimal contrasts for each will be generated. The hypotheses are as follows:

Null hypothesis (H₀): Optimal contrasts $\mu \ge 0$ for all models

Alternative hypothesis (H_A): Optimal contrasts μ <0 for at least one model

where μ is the true event rate.

The underlying model will be an ANCOVA with dependent variable 'change from baseline to Week 12 (LOCF)', and independent variables will include:

- dose group as a factor variable with the placebo group as the reference level
- baseline score, i.e. baseline weekly average pain (NRS), as a continuous variable
- co-medication type.

The random error is assumed to be normally and independently distributed with constant variance. The parameter estimates of the difference between each dose group and placebo, least square (LS) Means estimates of change from baseline to Week 12 for each dose, standard errors, 95% unadjusted, 'Lalonde-type' asymmetric CI (i.e., lower limit of 1-sided 90% CI and upper limit of 1-sided 80% CI), and *P* values will be presented.

[figure not shown]
If the MCP test is statistically significant, then the MOD step will select the most appropriate model from hyperbolic E_{max} , sigmoidal E_{max} or linear using the ' E_{maxlin} ' approach as described by Kirby et al (2011). From this model (including the same covariates as the ANCOVA model), various estimates will be derived (together with CI) of parameters of interest such as ED50, effective dose to achieve 90% of maximum effect (ED90), dose to achieve selected target effects, and model estimates of the treatment effect at doses studied (see Appendix in Section 15).

MMRM: In addition, changes from baseline in continuous endpoints will be compared between treatment groups using mixed models repeated measures including terms for:

- co-medication type (as a factor)
- treatment (as a factor)
- time (as a factor)
- the interaction between treatment and time point
- and the baseline value of the variable undergoing analysis

The mixed model for repeated measure will use average of average daily pain score of observed data at week 2, 4, 6, 8, 10, and 12. An unstructured covariance matrix will be used to model the

AD-ST-33.06 Effective date: 12-Nov-2020

within-subject errors. The Kenwards-Roger method will be used to estimate degrees of freedom. If this analysis fails to converge, a simpler structure (e.g., first-order ante-dependent or heterogeneous compound symmetry structures) will be found using Akaike information criterion (AIC).

The results will be presented using LS Means estimates, corresponding 95% CI for each treatment group and timepoint, along with the LS Means of differences with Placebo, standard error, 95% CI and p-values.

The primary efficacy analysis will be based on the mITT population.

8.1.1. Sensitivity Analyses of the Primary Efficacy Endpoint

To complement the MCP-MOD outputs, estimates and CI of each pairwise comparison versus placebo from the ANCOVA model described in the MCP step will be produced.

8.2. Secondary Efficacy Analysis

The MMRM model outlined in Section 8.1 will be applied for secondary endpoints using observed cases:

[figure not shown]
- Change in Galer NPS total score from baseline to Days 28, 56, and 84 of treatment and the follow-up visit.
- Change in DSIS from baseline to Days 28, 56, and 84 of treatment and the follow-up visit.
- Change in the eight SF-36 parameters from baseline to Day 84 of treatment.

A GEE approach for binary data will be used for the following dichotomous endpoints:

- Percentage of subjects who have achieved ≥30% reductions in the weekly average of the average daily pain score from baseline during Weeks 4, 8, and 12 of treatment and the week before follow-up.
- Percentage of subjects who have achieved ≥50% reductions in the weekly average of the average daily pain score from baseline during Weeks 4, 8, and 12 of treatment and the week before follow-up.

The GEE model specification will include a binomial distribution, a logit link function, and an unstructured covariance matrix. If this analysis fails to converge, a simpler structure (e.g. first-order autoregressive or compound symmetry structures) will be found using AIC. The model will include terms for:

- co-medication type (as a factor)
- treatment (as a factor)
- time (as a factor)
- the interaction between treatment and time

A CMH test stratified by the crossing of co-medication subgroup and median baseline pain score will also be carried out for the above dichotomous endpoints. The CMH risk difference at Week 12 will be estimated between the treatment group and placebo. The number and percentage of subjects meeting the reduction response will be displayed, along with the risk difference, 95% CI and *P* value.

[figure not shown]
The proportion of subjects who have 'improved', 'much improved,' or 'very much improved' relative to baseline on the PGIC on Days 28, 56, and 84 of treatment and the follow-up visit will be tested using a CMH statistics.

The efficacy analysis of secondary endpoints will be based on the observed cases and on the mITT population.

Usage of rescue medication (yes/no) will be summarized by dose group for each visit from baseline to Week 12 of treatment and over the whole treatment period. The following additional variables will be derived and summarised:

- Total number of days rescue medication was used.
 - Each day on which rescue medication was used at least once is counted.
- Cumulative consumption (mg) of paracetamol rescue medication use.
 - Calculated as the total dose of rescue medication (mg).
- Average daily dose (mg) of paracetamol rescue medication use.
 - Calculated as: cumulative consumption of rescue medication (mg)/total number of days rescue medication was used.

[figure not shown]

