6.1.2. Adjustments for Covariates

In addition to treatment group, the baseline value of the variable undergoing analysis and the co-medication type (Anticonvulsant versus Antidepressant) will be included in the analysis of covariance (ANCOVA) model as additive covariates. Co-medication type will be determined by blinded clinical review of each subject's medication record at baseline.

Covariates in the mixed effects models repeated measures (MMRM) and generalized estimating equations (GEE) analyses include those specified for the ANCOVA analyses, together with time and its interaction with dose group.

The crossing of co-medication type and median baseline pain score will be used as strata in the Cochran-Mantel-Haenszel (CMH) model tests. Assuming two co-medication types, the strata will be:

[figure not shown]
- 1) Anticonvulsant (Baseline NRS < Median),
- 2) Anticonvulsant (Baseline NRS > Median),
- 3) Antidepressant (Baseline NRS < Median),
- 4) Antidepressant (Baseline NRS > Median).

Where the median baseline NRS is calculated over all subjects.

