^[1] Common effect for the strata (co-medication type*median Baseline Pain NRS) specific risk difference, representing common difference in probability across strata.

^[2] P-value < 0.05 indicates a significant association between number of subjects with >=30% decrease from Baseline and treatment across strata. Reference Listing: 16.2.6.1

[figure not shown]

Table 14.2.6.2 Daily Pain NRS Responder Analysis (≥30%): GEE Analysis (Observed Cases) mITT Population

Model parameter estimates

Parameter	Estimate	Z value	Degrees of freedom	Standard Error	2-sided 95% CL	2-sided P-value [2]
Intercept	XX.XX	XX.XX		XX.XXX		•
Co-medication type			XX			0.xxxx
Week			4			0.xxxx
Treatment			3			0.xxxx
Treatment*Week			12			0.xxxx
Active 5 mcg vs Placebo	XX.XX	XX.XX	1	XX.XXX	[x.xx to x.xx]	0.xxxx
Active 150 mcg vs Placebo	XX.XX	XX.XX	1	XX.XXX	[x.xx to x.xx]	0.xxxx
Active 450 mcg vs Placebo	XX.XX	XX.XX	1	XX.XXX	[x.xx to x.xx]	0.xxxx
Dispersion	XX.XX					

CL = Confidence limits; GEE: Generalized Estimation Equations; NRS = Numeric rating scale.

Reference Listing: 16.2.6.1

Programming notes:

- Include all observed data for Week 4, 8, 12, and 18.
- Rows for column dosing (column dosing will only be added if Stage 4 is initiated.

Final 1.0 | 12-Jul-2023 | Page 48 of 205

^[1] Lower limit of 1-sided 90% CL and upper limit of 1-sided 80% CL.

^[2] P-value is derived from the following model: GEE using Time, Treatment, Treatment*Time and Co-medication type as covariates, with dependent binary variable indicating whether weekly average pain NRS has >=30% decrease from Baseline.

[figure not shown]

Table 14.2.7.1 Daily Pain NRS Responder Analysis (≥50%): Cochran-Mantel Haenszel (Observed Cases) mITT Population

Cochran-Mantel-Haenszel Test

Visit/	Number of		95% CI of Risk	2-sided
Category	Subjects (%)	Risk Difference [1]	Difference	P-value [2]
Week 4			•	
>=50% decrease from Baseline	xx (xx.x%)	X.XX	[x.xx to x.xx]	0.xxxx
Week 8				
>=50% decrease from Baseline	xx (xx.x%)	X.XX	[x.xx to x.xx]	0.xxxx
Week 12				
>=50% decrease from Baseline	xx (xx.x%)	X.XX	[x.xx to x.xx]	0.xxxx
	,			
Week 18	(0/)			0
>=50% decrease from Baseline	xx (xx.x%)	X.XX	[x.xx to x.xx]	0.xxxx

CI = confidence interval; NRS = numeric rating scale.

Programming notes:

• Include all observed data for Week 4, 8, 12, and 18.

^[1] Common effect for the strata (co-medication type*median Baseline Pain NRS) specific risk difference, representing common difference in probability across strata.

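### The responder GEE is specified with baseline pain in SAP Section 6.1.2 and without it in Section 8.2, and its fallback working correlation is to be chosen by AIC, which a GEE does not have

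*SAP*

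**What the plan says.** Section 6.1.2 of SAP v1.1 sets the covariates for all models. For the ANCOVA, "the baseline value of the variable undergoing analysis and the co-medication type (Anticonvulsant versus Antidepressant) will be included in the analysis of covariance" model as additive terms. It then says that the "generalized estimating equations (GEE) analyses include those specified for the ANCOVA analyses, together with time and its interaction with dose group". Section 8.1 identifies the ANCOVA baseline term as "baseline weekly average pain (NRS), as a continuous variable".

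Section 8.2 specifies the responder GEE itself: "The GEE model specification will include a binomial distribution, a logit link function, and an unstructured covariance matrix". Its list of model terms is co-medication type, treatment, time and, last, "the interaction between treatment and time". No baseline term appears. On non-convergence, "a simpler structure (e.g. first-order autoregressive or compound symmetry structures) will be found using AIC".

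In the version 1.0 table shells (12-Jul-2023), footnote [2] of Table 14.2.6.2 describes the model as "GEE using Time, Treatment, Treatment*Time and Co-medication type as covariates". The table has no baseline row, and the programming note for Table 14.2.7.2 repeats the same covariates for the 50% endpoint. The version 1.1 shells at hand stop before the efficacy tables, so the corresponding v1.1 table is not relied on here.

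**The concern.** Two programmers working from two sections of the same plan would fit different models to the same pre-specified endpoints. Which model was meant could then be settled after unblinding, with both results available.

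The fallback rule has a separate defect. It borrows the criterion that Section 8.1 uses for the MMRM, where a likelihood exists, and applies it to a method that has none. The candidate structures are given only as examples. If the unstructured fit fails, the plan therefore fixes neither the list of alternatives nor a usable way to choose among them. The fallback could be needed: Section 8.1 allows for stage 4 not being started, in which case Section 3.2 implies 28 + 60 = 88 evaluable subjects from stages 2 and 3. An unstructured matrix over four time points (Weeks 4, 8, 12 and the week before follow-up) has 4 × 3 / 2 = 6 correlations.

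**Working it through.** **1. Model terms side by side**

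| Source | Co-medication | Treatment | Time | Treatment × time | Baseline |
|---|---|---|---|---|---|
| Section 6.1.2, rule for GEE | yes | yes | yes | yes | yes |
| Section 8.2, GEE list | yes | yes | yes | yes | no |
| v1.0 shell, Table 14.2.6.2 | yes | yes | yes | yes | no |
| Section 8.1, MMRM list | yes | yes | yes | yes | yes |

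The MMRM list has the same four terms and adds baseline, so the GEE list is not shorthand. Section 10, which records departures from the planned analysis, does not mention dropping baseline from the GEE. SAP v1.0 has the same conflict between its Sections 6.1.2 and 8.2.

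**2. Which baseline.** A responder flag has no baseline value of its own. The flag is computed from the weekly average NRS. Baseline weekly average NRS is the ANCOVA covariate, and its median split defines the CMH strata for these same endpoints. That is the workable reading of Section 6.1.2.

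**3. AIC.** AIC = −2 log L + 2p, with L the maximised likelihood. A GEE solves estimating equations under a working correlation and has no joint likelihood. Some software prints a figure all the same. One illustrative binomial GEE with exchangeable working correlation had p = 8 (intercept 1, treatment 1, visit 3, treatment by visit 3) and a reported log-likelihood of −392.467. The printed AIC is 2 × 392.467 + 2 × 8 = 800.93. That log-likelihood is the one for independent observations; the working correlation is not in it. The figure therefore cannot rank first-order autoregressive against compound symmetry. QIC for the same fit was 788.70.

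**4. Size.** The plan gives no figure to reproduce. From SAP Section 3.2: group sizes 81 and 67, difference 1.25, SD 2.4, placebo reduction 1 point. Assumed: baseline about N(6.5, 1.3) limited to 4–9.5, and the slope of change on baseline.

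- *Week 12 logistic regression, 1,500 trials per slope.* At four slopes running from −0.35 to +0.6, power without and with baseline was 71.0% and 71.3%, 70.7% and 70.7%, 65.9% and 68.9%, 62.0% and 66.0%. The differences are 0.3, 0.0, 3.0 and 4.0 points. In a separate run with 1,200 trials per slope, slopes from −0.5 to 0 gave changes below 2 points in either direction.
- *Shift in a single trial's z value (the 1,200-trial run, 30% threshold).* Median 0.03, 0.07 and 0.24, and 95th percentile 0.17, 0.30 and 0.74, at slopes −0.35, 0 and +0.6.
- *The GEE itself (exchangeable, Weeks 4, 8, 12 and 18, no co-medication term, 150 runs per setting).* Mean Week 12 log odds ratio without and with baseline was 0.905 and 0.913, 0.871 and 0.886, 0.887 and 0.981, when the assumed correlation of higher baseline with larger reduction was 0, 0.3 and 0.5. Power was 76.7% and 76.7%, 68.7% and 71.3%, 78.7% and 80.0%. With 150 runs the Monte Carlo standard error of one power figure is about √(0.75 × 0.25 / 150) = 3.5 points, so these agree with the logistic results but do not sharpen them.

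At correlation 0.5 the odds ratio moves from exp(0.887) = 2.43 to exp(0.981) = 2.67. That is a change of estimand, from averaged over baseline to conditional on it, and not a correction of bias.

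**The case against.** Section 6.1.2 speaks of the baseline of the variable being analysed, and a binary flag has none. Section 8.2 is the endpoint-specific text, so one could say that it simply governs. This stands to the extent that reading baseline NRS into Section 6.1.2 is an inference. It does not remove the conflict, because Section 6.1.2 names the GEE explicitly and no rule says which section prevails.

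A reader might infer that, because response is a percentage of baseline, it must depend on baseline pain. That does not follow. If change = a − 0.3 × baseline + error, the 30% criterion reduces to a + error ≤ 0, which is free of baseline. The near-zero gain at slope −0.35 shows this.

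A reader might also infer that chance imbalance under unstratified randomisation biases the result. Under randomisation it does not bias the comparison on average or inflate type I error. The same endpoints also get a CMH analysis stratified by median baseline pain and co-medication, so a baseline-adjusted result is already planned.

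The largest z shifts, about 0.74, should not be quoted as typical. They belong to slope +0.6, where Week 12 pain would rise 1 + 0.6 = 1.6 points per baseline point; about 17% of simulated Week 12 scores then fell outside 0–10.

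Finally, the AIC sentence operates only if the unstructured fit fails, and with robust standard errors and complete data the working structure affects efficiency, not validity. That limits the harm. It does not make the rule workable, and because the analysis uses observed cases, dropout can make the estimate depend somewhat on the structure chosen.

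**Conclusion.** Both points hold in SAP v1.1 on Sections 6.1.2 and 8.2 alone; the v1.0 shell is supporting evidence only. The plan specifies two different responder GEE models, and its fallback criterion is not defined for a GEE.

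The reach is limited to the two secondary responder endpoints. The expected power change is about 0 to 4 points over the assumed slopes and under 2 at plausible ones. These figures rest on an assumed baseline distribution and assumed slopes, and the power range comes from a single-visit logistic model without co-medication. Nothing here touches the primary MCP-Mod test or the sample size. The documents do not support a claim that the responder comparison is biased or left without any baseline adjustment. The case for acting is that the model and its fallback should be fixed before unblinding, at almost no cost.

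**What to change.** In Section 8.2, add baseline weekly average pain NRS as a continuous covariate to both responder GEE models, and add the matching row and footnote to shell Tables 14.2.6.2 and 14.2.7.2. State that the treatment odds ratio is then conditional on baseline. If baseline was left out on purpose, for instance to keep an odds ratio averaged over baseline, exempt the GEE in Section 6.1.2 and give the reason. Either route resolves the conflict.

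Replace AIC by QIC, in the form whose penalty uses the robust covariance, or by a fixed order of fallback structures with no data-driven choice. Close the list of candidates, and state that inference uses robust (sandwich) standard errors; the plan neither requires nor excludes them.

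The cost is SAP and shell wording with minor programming. Baseline NRS is already collected and derived, so no further data are needed.

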6.1.7.6. Rescue Medication Use

Subjects will record all rescue medications they take for neuropathic pain in a paper diary. This will be transcribed in to the eCRF collecting usage, date and time of rescue medication, medication administered, dose, frequency and route.

Subjects will be grouped by the following for rescue medication use:

- Compliant with protocol guidance on permitted therapies
- Non-compliant with protocol guidance on permitted therapies

A review of medications will be conducted at a blinded data review meeting to be held before the study database is locked.

[figure not shown]

AD-ST-33.06 Effective date: 12-Nov-2020

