6.1.8. Derived Variables

- Change from baseline = value at current time point value at baseline.
- Reference End Date = Date of completion/discontinuation.
- Study duration = Reference end date date of first dose of treatment + 1
- Duration of exposure (days) = min(date of last dose of treatment + 14 days or date of death) date of first dose of treatment + 1.
- Treatment-emergent AEs (TEAEs) are defined as:
 - o AEs with onset at the time of or following the start of treatment with IP, or
 - AEs starting prior to the start of treatment but increasing in severity or relationship at the time of, or following, the start of treatment with IP.
- Average Baseline Pain NRS = the arithmetic average of the 'non-missing' daily pain scores within the baseline period defined in Section 6.1.1. For example, if a subject has 5 days of non-missing pain scores their average will be calculated over 5 days, not the full 7-day baseline period.
- Average Week X Pain NRS = the arithmetic average of the 'non-missing' daily pain scores within each subject's specific week X period defined in Section 6.1.5.
- Average Week 12 Pain NRS (LOCF) = the arithmetic average of the 'non-missing' daily pain scores within each subject's specific week 12 period or according to the imputed LOCF/BOCF approach defined in Section 6.1.4.
- Change from Baseline to Week X Pain NRS = for each subject 'Average Week X Pain NRS' minus 'Average Baseline Pain NRS'.
- Change from Baseline to Week 12 Pain NRS (LOCF/BOCF) = for each subject 'Average Week 12 Pain NRS (LOCF)' minus 'Average Baseline Pain NRS'.
- Galer NPS Total Score (ranges from 0 to 100): sum of Pain Intensity, Pain Unpleasantness, Pain Sharpness, Pain Hotness, Pain Dullness, Pain Coldness, Pain Sensitivity, Pain Itching, Deep Pain Intensity, and Surface Pain Intensity (All in an 11-point NRS).
- Change from Baseline to Week X Galer NPS Total Score = for each subject 'Galer NPS Total Score' minus 'Baseline Galer NPS Total Score'.
- Total number of days rescue medication was used = End Date of Medication Start Date

of medication + 1. Each day on which rescue medication was used at least once is counted.

- Cumulative consumption (mg) of paracetamol rescue medication use = Total dose of rescue medication (mg) consumed during the days in which paracetamol was used.

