- Average daily dose (mg) of paracetamol rescue medication use = Cumulative consumption of paracetamol rescue medication (mg) /total number of days paracetamol rescue medication was used.

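### SAP v1.1 gives conflicting rules for average daily paracetamol dose (6.1.8 against 8.2) and for days of rescue use (within one 6.1.8 bullet)

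*SAP*

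**What the plan says.** All references are to SAP v1.1 unless stated.

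- **Collection (6.1.7.6).** "Subjects will record all rescue medications they take for neuropathic pain in a paper diary". The eCRF then takes "date and time of rescue medication, medication administered, dose, frequency and route". Use is sorted into a compliant group and one labelled "Non-compliant with protocol guidance on permitted therapies".
- **Days of rescue use (6.1.8).** "Total number of days rescue medication was used = End Date of Medication Start Date", continuing "of medication + 1. Each day on which rescue medication was used at least once is counted". The minus sign is missing in the text available here, as it is in the study-duration line of the same list. It is read as a minus, and its absence is not part of this point.
- **Average daily paracetamol dose (6.1.8).** Cumulative paracetamol consumption in mg over the "total number of days paracetamol rescue medication was used".
- **The same variables in 8.2.** "Total number of days rescue medication was used" stands as a variable of its own, with the counting rule only. Average daily paracetamol dose is "Calculated as: cumulative consumption of rescue medication (mg)/total number of days rescue medication was used". The bullet before it, cumulative paracetamol consumption, is also calculated as a total of rescue medication, without the word paracetamol.
- **Table 14.2.5.1 (v1.0 shells; the v1.1 shells at hand stop before this table).** Footnote 1 counts days of permitted rescue only. Footnote 3 divides paracetamol mg by days of rescue use. Subjects with prohibited rescue have a separate row.
- **Listing 16.2.6.5 (v1.0 shells).** Rescue records are shown with start and end dates, dose and frequency. Some starts are month-only and some records are still ongoing.

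**The concern.** A derivation section should give one rule per variable. Here average daily paracetamol dose has one divisor in 6.1.8, another in 8.2, and a third variant in the visible shell. The 8.2 divisor is hard to dismiss as loose wording, because it repeats the name of a variable that both sections define separately and that is not limited to paracetamol. A programmer working from 8.2 has good reason to use that variable.

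The day count has the same problem within one bullet. A date span includes days without use inside a record. Added over records, it also counts overlapping days more than once. A count of days with at least one use does neither.

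Two programmers following the text could therefore report different days and different doses from the same records. The estimand in 2.2.1.1 is stated regardless of rescue use, so readers will look to these summaries when interpreting the pain result.

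**Working it through.** The SAP states no figure for these variables, so there is none to reproduce. The rules are applied to assumed subjects. Every usage pattern below is an assumption.

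**Average daily dose.** Let P be paracetamol mg, O the mg of other rescue drugs, dp the days with paracetamol and dr the days with any rescue. The 6.1.8 numerator is taken as P, as its average-dose bullet names it.

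- 6.1.8: P/dp
- Shell footnote 3: P/dr, where footnote 1 limits dr to permitted rescue
- 8.2 read literally: (P + O)/dr

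Assumed subject: 2,000 mg paracetamol on 24 days, so P = 48,000 and dp = 24, plus another rescue drug on 6 other days, so dr = 30.

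- 6.1.8: 48,000/24 = 2,000 mg/day.
- P/dr, if the other drug is permitted or all rescue counts: 48,000/30 = 1,600 mg/day.
- P/dr, if the other drug is prohibited and footnote 1 applies: the 6 days drop out, and 48,000/24 = 2,000 mg/day.
- 8.2 read literally: (48,000 + O)/30. This equals 2,000 when O = 30 × 2,000 − 48,000 = 12,000 mg. It is lower for smaller O and higher for larger O.
- If every rescue day includes paracetamol (dr = dp = 24), literal 8.2 is (48,000 + O)/24, which exceeds 2,000 for any O above zero.

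With a paracetamol numerator, and a share s of counted rescue days without paracetamol, the result is 2,000 × (1 − s): 2,000, 1,800, 1,500 or 1,000 mg/day for s = 0%, 10%, 25% or 50%.

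**Days of rescue use.** Assume one record from Day 1 to Day 84, with use on k days a week for 12 weeks. The count is 12k. The date formula is 84 − 1 + 1 = 84.

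| Days a week | Count | Date formula | Ratio |
|---|---|---|---|
| 7 | 84 | 84 | 1.0 |
| 5 | 60 | 84 | 1.4 |
| 3 | 36 | 84 | 2.3 |
| 2 | 24 | 84 | 3.5 |
| 1 | 12 | 84 | 7.0 |

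Overlap: records for Days 1–10 and 6–15 give 10 + 10 = 20 if spans are summed, against 15 distinct days.

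**Both together.** Put the first subject's paracetamol in one Day 1 to Day 84 record and the other drug in six one-day records. Total days are 24 + 6 = 30 by count and 84 + 6 = 90 by summed spans, which is more than the 84-day window. A paracetamol numerator over 90 gives 48,000/90 = 533 mg/day.

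The rules agree when paracetamol is the only rescue drug, records do not overlap, and every day within a record has use.

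**The case against.** The best reply is that 8.2 is shorthand. Its bullet is headed as paracetamol, and if both terms inherit that word, 8.2 equals 6.1.8. Section 6.1.8 is loose in a similar way: its cumulative-consumption bullet speaks of the total rescue dose on paracetamol days. That reading is possible. It does not settle the matter, because the 8.2 divisor carries another variable's name and the visible shell pairs a paracetamol numerator with rescue days.

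On days, the count appears three times (6.1.8, 8.2, shell footnote 1) and the date formula once, so the count is plainly the intended rule. The formula could also be meant as the length of a single record, with the next sentence ensuring that each day counts once. That would remove the overlap example but not the intermittent-use one.

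Two stronger readings are tempting and are not supported:

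- A reader might infer that 8.2 always gives a lower average, or an equal one when every rescue day includes paracetamol. That needs a paracetamol-only numerator, which 8.2 does not state. Read literally, it can be higher or lower.
- A reader might infer from the non-compliant group that days on prohibited drugs enter the divisor. Shell footnote 1 would exclude them. The rules then differ only if a permitted rescue drug other than paracetamol exists, and the list of permitted therapies is not in this document.

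**Conclusion.** The inconsistency is real and minor. Average daily paracetamol dose has competing definitions that can differ once other rescue drugs are used. Days of rescue use has two rules in one bullet; the date rule overstates days for intermittent use and, if spans are summed, for overlapping records.

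The sizes above (1,600 against 2,000 mg/day; 30 against 90 days; ratios up to 7.0) depend on assumed patterns. They show what the text allows, not what the trial will find. The 1,600 and 533 mg/day figures further assume a paracetamol numerator.

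A reader might infer that an efficacy conclusion is at risk. It is not. Section 2.2.1.2 names rescue use as a yes/no endpoint, which neither rule touches. Days and mg are additional descriptive variables, and no test or primary result uses them.

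**What to change.** 1. In 8.2, state cumulative consumption and average daily dose with a paracetamol numerator, and divide the latter by distinct days with at least one paracetamol use, in line with 6.1.8.
2. In 6.1.8, delete the date formula and keep the count of distinct calendar days with at least one use.
3. State whether rescue days cover all rescue medication or only permitted rescue, and make the Table 14.2.5.1 footnotes match.
4. Where the data hold only start and end dates with a frequency, or an ongoing record, as Listing 16.2.6.5 allows, footnote that distinct days cannot be fully recovered.

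The cost is a few SAP lines and matching table footnotes. The count needs dates of use, which 6.1.7.6 says are collected; item 4 covers records where they are not available day by day.
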